13.6 Analysis of secondary outcomes

All outcomes will be reported descriptively for all data collection timepoints.

The PEM Hand Health Profile subscale will be extracted from the primary analysis model at six-weeks and three-months post-randomisation.

Continuous outcome measures will be analysed in a similar way to the primary outcome, swapping baseline PEM Hand Health Profile score with the baseline value of the outcome as a covariate. If the measure was not completed at baseline (PEM treatment subscale, PEM Overall assessment, ROM and Grip strength) no adjustment will be made.

Adherence to the splint regimen at six-weeks post-randomisation will be summarised descriptively, by trial arm and overall, using counts and percentages for items one to four, and a mean and standard deviation for item five.

Adherence to the therapy regimen at six-weeks and three-months post-randomisation will be summarised descriptively, by trial arm and overall, using counts and percentages.

Treatment and outcome satisfaction will be analysed descriptively.

Complications (including deep wound infection (Yes/No), tendon rupture (Y/N), superficial infection (Yes/No) and rehospitalisation (Yes/No)) and further surgical procedures (Y/N) will be analysed using

a separate logistic regression models including similar covariates as the primary analysis model providing there are a minimum number of events (at least 5 per arm).

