5.5.4 Statistical Analysis

For the analysis of the main trial, a CONSORT flow diagram will be provided to display the flow of participants through the study. The number of participants withdrawing from the trial will be summarised with reasons where available.

Baseline characteristics will be presented descriptively by group. All outcomes will be reported descriptively at all collected time points. Continuous data will be presented using means and standard deviations or medians and ranges as appropriate, and categorical data will be presented using frequencies and percentages.

The primary analysis will be on an intention-to-treat basis, analysing participants in the groups to which they were randomised. We will compare the Patient Evaluation Measure (PEM) scores between groups using a covariance pattern mixed-effect linear regression model, incorporating postsurgery time points (six weeks, three and six months). Treatment groups, time point, treatment-bytime interaction and baseline covariates (such as digital neve injury and anaesthetic type) will be included as fixed effects. Participant will be included as a random effect accounting for repeated

FLARE Protocol Page 33

Version 1.1

observations per patient. Estimates of the difference in PEM scores will be extracted for each time point (primary six months) and overall with two sided 95% Cis (equivalent to a one-sided 97.5% CI) and p-values. Completeness of data at follow-up will be reported by group. In non-inferiority comparisons the ITT analysis could bias towards the null, which may lead to false claims of noninferiority, hence we will undertake both ITT and CACE (complier average causal effect) analyses.

Total range of movement will be analysed using a similar covariance pattern model as used for the primary analysis. Differences in binary outcomes (e.g., tendon ruptures, re-operation and surgical site infection) will be analysed by logistic regression models. Differences in grip strength will be analysed by a linear regression model. Adverse events will be reported by allocation and overall, with further summaries of this data by type of event, relatedness to study treatment and expectedness. Treatment and outcome satisfaction will be analysed descriptively.

Full analyses will be detailed in the trial's statistical analysis plan (SAP), which will be reviewed and approved by the trial steering and data monitoring committees and finalised before the end of participant follow-up.

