13.5 Primary analysis

The primary outcome measure (PEM Hand Health Profile) will be reported descriptively, by trial arm and overall, for all data collection timepoints (baseline, six-weeks, three-months and six-months postrandomisation).

The primary analysis will compare PEM Hand Health Profile scores between treatment groups using a covariance pattern mixed effect linear model, incorporating data from all post-randomisation time points (six-weeks, three-months and six-months). The model will adjust for digital nerve injury, anaesthetic type, baseline PEM Hand Health Profile score (both pre and post-injury), time, treatment arm, treatment-by-time interaction as fixed effects, with site and participant as random effects to account for clustering by site and repeated observations per participant.

The correlation of observations within participants over time will be modelled by a covariance structure. The different covariance structures for repeated measurements that are available as part of the analysis software will be applied to the model. The Akaike information criterion will be used to compare models specifying different covariance structures with smaller values preferred. Model assumptions will be checked as follows: the normality of the standardised residuals will be assessed using a QQ plot, and homoscedasticity will be assessed by means of a scatter plot of the standardised residuals against fitted values. One possible violation of the assumptions may be the normality of the residuals due to a potential ceiling or floor effect where a lot of patients have a score of zero. In this instance, we will carry out an additional sensitivity analysis using a semi-parametric approach based on an ordinal regression model using the 'glm' Stata command with a logit link function.

Participants will only be included in the model if they have complete data for the baseline covariates and a valid PEM Hand Health Profile score for at least one post-randomisation timepoint.

The treatment effect at all time points (six-weeks, three-months and six-months) and overall will be extracted in the form of an adjusted mean difference, two-sided 95% CIs (equivalent to a one-sided 97.5% CI) and p-value. The primary timepoint of interest is six-months post-randomisation. A detailed description of how we will interpret the treatment effect estimate is included in Appendix A.

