17.3.4 Treatment delivery

Table 15:	Treatment	received	presented	by ra	andomised	treatment group
-----------	-----------	----------	-----------	-------	-----------	-----------------

	Randomise	d treatment	
	Intervention (n=) Control (n=)		
Treatment received			
Intervention			
Control			
Other			

 Table 16: Primary surgery data presented by randomised treatment group

	Interventio	Control	Overall
	n (n=)	(n=)	(n=)
Injury Details			
Sub zone of injury, n (%)			
2A			
2B			
2C			
2D			
Digital nerve injury, n (%)			
Partial			
Complete			
No nerve injury			
Nerve damaged, n (% of partial or complete injury)			
Ulnar			
Radial			
Digital nerve repaired, n (% of partial or complete			
injury)			
Nerve suture repaired			

Nerve ends laid inline but not sutured		
No repair		
Other		
Theatre Logistics		
Physical location of procedure, n (%)		
Main operating theatre with laminar flow		
Main operating theatre with air changes		
Minor operating room/procedure room		
Trauma clinic / outpatient room		
Emergency department room		
Other		
Duration of operation (mins)		
N (% data available)		
Mean (SD)		
Median (IQR)		
(Min, Max)		
Type of anaesthetic, n (%)		
Local anaesthetic alone (without adrenaline)		
Local anaesthetic with adrenaline		
Upper limb block alone		
General anaesthetic and upper limb block		
General anaesthetic and local anaesthetic		
General anaesthetic alone		
Tourniquet used in (%)		
Yes		
No		
Tourniquet placed n (%)		
Arm		
Forearm		
Length of time tourniquet annlied (mins)		
N (% data available)		
Mean (SD)		
Median (IOR)		
(Min Max)		
Prophylactic antibiotics at induction n (%)		
No		
Surgical Papair of EDP		
Surgical Repair of FDP		
Adelaida		
Adeiaide Medified Keesler		
Crucieto		
Million		
M-Tally Other		
Other		
Core suture number of strands of FDP, n (%)		
4		
Core type of suture of FDP, n (%)		
Prolene		
Polydioxanone suture (PDS)		

Fibrewire			
Ti Cron			
Other			
Core suture size of FDP, n (%)			
2-0			
3-0			
4-0			
5-0			
Other			
Epitendinous suture for FDP, n(%)			
Yes			
No			
Epitendinous suture technique for FDP, n (%)			
Simple continuous			
Silverskold			
Other			
Epitendinous type of suture for FDP, n (%)			
Prolene			
Polydioxanone suture (PDS)			
Fibrewire			
Ti Cron			
Other			
Epitendinous suture size for FDP, n (%)			
2-0			
3-0			
4-0			
5-0			
6-0			
Pulleys surgically vented, n (%)			
Yes - A1			
Yes - A2			
Yes - A3			
Yes - A4			
No			
Other			
Surgical Repair of FDS			
Core tendon repaired			
Yes			
No			

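### The five-events-per-arm condition in SAP 13.6 removes the formal comparison of complications where the split between arms is most unbalanced, and no fallback is named

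*SAP*

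**What the plan says.** Comparing the complications of the two repairs is a secondary objective (Protocol 2.2, Table 6; SAP 4.2, item d). On method, Protocol 5.5.4 states: "Differences in binary outcomes (e.g., tendon ruptures, re-operation and surgical site infection) will be analysed by logistic regression models". It sets no minimum number of events.

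SAP 13.6 narrows this. Deep wound infection, tendon rupture, superficial infection, rehospitalisation and further surgical procedures each get a logistic model "including similar covariates as the primary analysis model providing there are a minimum number of events (at least 5 per arm"). No exact test, risk difference, interval or reduced model is named for outcomes that miss the condition.

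The covariates are those of SAP 13.5: "The model will adjust for digital nerve injury, anaesthetic type, baseline PEM Hand Health Profile score (both pre and post-injury), time, treatment arm", "with site and participant as random effects to account for clustering by site and repeated observations per participant". SAP 13.6 does not say which of them the word similar keeps, or how they are coded. The only full lists of levels for the surgical variables are in the Table 16 shell. "Digital nerve injury, n" has three levels (partial, complete, none). "Type of anaesthetic, n" has six, beginning with "Local anaesthetic alone (without adrenaline").

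Descriptive reporting is unconditional: "All outcomes will be reported descriptively for all data collection timepoints". The Table 25 shell shows complications by arm at each follow-up.

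**The concern.** A minimum count is normally there to stop an unstable model being fitted. Stability depends on total events relative to the number of parameters, and on whether any covariate level has no events. A rule on the smaller arm measures something else: it is also triggered by imbalance between arms, which is the quantity of interest. An outcome with many events in one arm and few in the other fails, while one with few events in both can pass.

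The safety comparison is at stake. Protocol 1.1 cites a small comparative study with more reoperation for rupture or adhesions when both tendons were repaired. Protocol 4.10.2 records patients' safety concerns about not repairing both. A large difference in either direction would matter to readers, yet the plan may supply no estimate or interval for it. Any comparison made after seeing the counts would then be post hoc.

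**Working it through.** **Arm sizes.** Protocol 5.5.2 and SAP 9 give a margin of 7, SD 17, one-sided alpha 0.025, 90% power and 20% attrition.
- n per arm = 2 × 17² × (1.960 + 1.282)² / 7² = 123.9, rounded up to 124.
- Total = 248; 248 / 0.80 = 310, which reproduces the plan's figure.
- So there are 155 per arm as randomised and 124 after the planned attrition.

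**Splits that are and are not compared** (155 per arm, two-sided Fisher exact test):

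| Events | Fisher p | At least 5 in each arm? |
|---|---|---|
| 0 v 6 | 0.030 | No |
| 0 v 10 | 0.0017 | No |
| 4 v 13 | 0.043 | No |
| 4 v 20 | 0.0010 | No |
| 5 v 5 | 1.0 | Yes |
| 5 v 15 | 0.035 | Yes |

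**How often the condition fails.** P(fail) = 1 − P(X₀ ≥ 5) × P(X₁ ≥ 5), with each X binomial. For 2% v 10% at 155 per arm this is 1 − 0.2002 × 0.9996 = 0.80. All true rates below are assumptions. The nearest figure in the documents is the re-repair rate of up to 17% in Protocol 1.2.

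| True rates | P(fail), 155 per arm | P(fail), 124 per arm |
|---|---|---|
| 2% v 10% | 80% | 90% |
| 3% v 10% | 50% | 69% |
| 5% v 10% | 11% | 26% |
| 5% v 5% | 21% | 44% |
| 10% v 17% | 0.04% | 0.4% |
| 17% v 17% | about 0% | about 0% |

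At 155 per arm, the probability that the condition fails and Fisher p is below 0.05 in the same trial is 72% at 2% v 10%, 43% at 3% v 10% and 2% at 5% v 5%.

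**What an unconditional interval would show.** For 4 v 20 of 155 the risks are 2.6% and 12.9%. The Wilson limits, (p + z²/2n ± z√(p(1−p)/n + z²/4n²)) / (1 + z²/n), are 1.0% to 6.4% and 8.5% to 19.1%. Combining them by Newcombe's method:
- difference = 12.9 − 2.6 = 10.3 points;
- lower limit = 10.3 − √((12.9 − 8.5)² + (6.4 − 2.6)²) = 4.5;
- upper limit = 10.3 + √((19.1 − 12.9)² + (2.6 − 1.0)²) = 16.7.

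The SAP plans no such figure for this split.

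**Events per parameter at the minimum of 5 + 5 = 10 events** (intercept and site variance not counted; the time terms do not carry over to a single yes/no outcome):
- Table 16 levels with both PEM scores: treatment 1 + nerve 2 + anaesthetic 5 + PEM 2 = 10 parameters; 10/10 = 1.0.
- Table 16 levels without PEM: 8 parameters; 10/8 = 1.25.
- Nerve and anaesthetic both binary, with PEM: 5 parameters; 10/5 = 2.0.
- Both binary, without PEM: 3 parameters; 10/3 = 3.3.

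As an illustration, I simulated Table 16 levels with assumed shares (nerve 50/20/30%; anaesthetic 10/30/25/15/10/10%). At least one level had no events in about 87% of 5 v 5 datasets and 37% of 10 v 10 datasets. These figures depend on the assumed shares and on keeping all six anaesthetic levels.

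**The case against.** The strongest reply is that nothing is hidden. A reader might infer that the rule suppresses lopsided safety results. The documents do not support that: SAP 13.6 reports every outcome descriptively, and Table 25 would print 4 and 20 side by side. The data monitoring committee also reviews safety data and may see it unblinded (Protocol 5.6.4). This stands. The loss is confined to the estimate, interval and test.

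Second, the high failure rates need one arm to be at about 2% or 3%, and no document gives such a rate. If both arms were near 17%, or at 10% v 17%, the condition would almost never fail. This stands too, and is why a range is shown. For outcomes rare in both arms, failure costs little, since any comparison would be imprecise.

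Third, a reader might infer that the permitted models generally run at one event per parameter. That holds only at exactly 10 events with full Table 16 coding. Table 16 is a descriptive shell, the SAP asks for similar rather than identical covariates, and the ratio rises with the count. At 17% in both arms (about 52 events) it is about 5 even with 10 parameters.

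Finally, one might be tempted to call re-rupture the main safety question about leaving FDS unrepaired. The documents do not say so: the study cited in Protocol 1.1 points the other way, and Protocol 1.3 frames the trade-off as strength against movement.

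None of this supplies a fallback, or a reason for the rule to act on the smaller arm.

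**Conclusion.** The point holds in limited form. For complications and further surgery, SAP 13.6 makes the only planned formal comparison depend on the smaller arm's count. It therefore withholds the estimate, interval and test from splits as unbalanced as 4 v 20 or 0 v 10 while allowing 5 v 5. Those examples need only 155 per arm. How often it would happen rests on assumed event rates and runs from about 0% to 80% of trials over the range shown at full sample size. It matters for less common outcomes, or where one arm does much better than the other.

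The weakness of the model at the threshold is secondary: 1.0 to 3.3 events per parameter at 10 events, according to a coding that the SAP does not state. These are secondary outcomes with counts reported by arm, so the primary conclusion is unaffected. The change is still worth making, because comparing complications is a stated objective and the repair is cheap.

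**What to change.** Amend SAP 13.6 as follows.
1. Remove the per-arm minimum as a bar to comparison. For each listed complication and for further surgery, report the six-month cumulative risk in each arm and the risk difference with an exact or score 95% confidence interval, whatever the count.
2. Base any rule for fitting the adjusted logistic model on total events relative to the number of model parameters. The exact threshold, and whether to use a penalised fit, are for the trial statisticians to choose and state in advance.
3. List the covariates of the full and reduced models and their coding: how the nerve and anaesthetic levels are grouped, whether the PEM scores are kept, and how site, the only stratification factor, is handled.
4. Add a table shell for these results. Table 22 covers mean differences only, and Table 25 has counts by timepoint without a cumulative six-month row.

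The cost is SAP wording and a few lines of code, with no new data. The downside is that rare outcomes will carry an unadjusted comparison with a wide interval.

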13.7 Sensitivity analysis of the primary outcome

13.7.1 CACE analysis

In non-inferiority comparisons the ITT analysis could bias towards the null, which may lead to false claims of non-inferiority. For this reason a CACE (complier average causal effect) analysis will also be undertaken in addition to the ITT analysis.

A CACE analysis for the primary outcome will be conducted to obtain unbiased estimates of the intervention effectiveness in the presence of full compliance with the intervention for those allocated to the intervention i.e. outcomes analysed with participants in the treatment group for the treatment which they received, rather than were randomised to.

A two-stage least squares instrumental variable approach will be used (with treatment assignment as the instrumental variable) using the ivregress command in Stata, with the 2sls option (Dunn et al., 2005). This analysis will use a linear regression model for the PEM Hand Health Profile score at six-months, adjusting for baseline score, and with robust standard errors to account for clustering within site.

Data from the Primary surgery form will be used to define a 'complier' (based on the question 'Which treatment did the participant receive?'.

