5.5.2 Determination of Sample Size

There will be a 22-month recruitment period for the FLARE trial. The total target sample size will be 310 participants.

A six-point difference on the Patient Evaluation Measure (PEM) represents the threshold at which treatment differences become important (based on observational data from patients with Dupuytren's contracture for the DISC trial (HTA 15/102/04)). However, recent analysis within a flexor tendon population has found a seven-point difference on the PEM to be important and thus represents an appropriate non-inferiority margin to be used in this population. For 90% power and alpha=0.025, 310 participants are required to establish noninferiority within a margin of 7 points on the PEM (SD=17; upper 80% confidence limit (22)), based on the lower limit of a 95% two-sided confidence interval (equivalent to a one-sided 97.5% CI) and 20% attrition.

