8.2 Data collected via paper

Participants will be given the option to complete consent forms, baseline, and follow-up postal questionnaires on paper, if required. Paper consent forms and baseline questionnaires will be returned to sites to be recorded into the REDCap study management system. Paper follow-up questionnaires will be returned to YTU where data will be transferred into the REDCap study management system. Paper copies will be stored in a locked filing cabinet in a room with restricted access at the University of York.

9. Sample Size

A six-point difference on the PEM represents the threshold at which treatment differences become important (based on observational data from patients with Dupuytren's contracture for the DISC trial (HTA 15/102/04)). However, recent analysis within a flexor tendon population has found a seven-point difference on the PEM to be important and thus represents an appropriate non-inferiority margin to be used in this population. For 90% power and alpha=0.025, 310 participants are required to establish noninferiority within a margin of seven points on the PEM (SD=17; upper 80% confidence limit), based on the lower limit of a 95% two-sided confidence interval (equivalent to a one-sided 97.5% CI) and 20% attrition.

10. Randomisation

Eligible patients will be randomly allocated in a 1:1 ratio to receive either repair of both FDS and FDP or repair of FDP only using block randomisation stratified by study site with randomly varying block sizes. An independent statistician at YTU, who is not involved in the recruitment of participants, will generate the allocation schedule. The allocation schedule will be generated in Stata v17 or later.

Randomisation will be carried out using REDCap and be completed in theatre with treatment allocated on an individual patient basis.

11. Blinding

Patients will be blinded to treatment allocation and will not be told which type of tendon repair they have received. The resulting scar will not disclose the allocated intervention. A code break procedure for clinical care or safety reporting will be in place.

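### SAP 13.7.1 glosses the CACE analysis as an as-treated comparison, contradicting its own 2SLS specification, and its covariates do not match those of the primary model

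*SAP*

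**What the plan says.** SAP 13.7.1 and Protocol 5.5.4 add a CACE analysis for the same reason: ITT can pull a difference towards the null, "which may lead to false claims of non-inferiority". SAP 13.7.1 then describes the analysis in two ways.

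- Its second paragraph aims at the effect under full compliance and restates this as "outcomes analysed with participants in the treatment group for the treatment which they received, rather than were randomised to".
- Its third paragraph specifies 2SLS through Stata's ivregress, with randomised assignment as the instrument. The outcome is the six-month PEM Hand Health Profile score, "adjusting for baseline score, and with robust standard errors to account for clustering within site".

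The primary model in SAP 13.5 is a mixed model over six weeks, three months and six months, with site and participant as random effects. On covariates it says: "The model will adjust for digital nerve injury, anaesthetic type, baseline PEM Hand Health Profile score (both pre and post-injury". SAP 7.1 confirms that the baseline PEM is taken twice, once for the hand before injury and once after it. Under SAP 13.7.2 a participant with complete covariates enters the primary model with a single follow-up score from any visit.

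CACE is listed among the sensitivity analyses in SAP 13.7. The acceptance rule in Appendix A refers to the SAP 13.5 analysis.

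**The concern.** As-treated and instrumental-variable analyses are different estimators. Regrouping by treatment received compares groups that were no longer formed by randomisation. If participants who depart from allocation have a different prognosis, the estimate is biased, and in a non-inferiority trial the bias can favour the claim. 2SLS keeps the randomised groups and rescales their difference by the difference in receipt. Anyone who took the gloss literally would report the first quantity under the name of the second.

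The model raises a second issue. CACE is set beside ITT to show what non-compliance did to the estimate. That reading needs the two analyses to differ in compliance alone. As written, they also differ in covariates, in which baseline PEM score is used, and in which participants and visits contribute.

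**Working it through.** **Inputs.** SAP Section 9: "For 90% power and alpha=0.025, 310 participants are required to establish noninferiority within a margin of seven points on the PEM", with the interval described as "equivalent to a one-sided 97.5% CI) and 20% attrition". Protocol 5.5.2: "SD=17; upper 80% confidence limit (22". SAP Section 10: "randomly allocated in a 1:1 ratio". No rate of non-receipt is assumed anywhere, so the rates below are my assumptions.

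**1. The plan's own figure.** n per arm = 2 × (1.960 + 1.282)² × 17² / 7² = 124 after rounding up. Total 248, and 248 / 0.80 = 310. This matches exactly, so the sample size rests on SD 17 (SD 22 would need 208 per arm, or 520 after attrition). The standard error with 124 evaluable per arm is 17 × √(2/124) = 2.159.

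**2. What non-compliance does to ITT.** Let d be net non-receipt (1 minus the between-arm difference in receipt), and let the true harm of FDP alone be exactly 7 points. The ITT difference is 7(1 − d), and the false non-inferiority rate is Φ(7d / 2.159 − 1.96).

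| d (assumed) | ITT difference | False non-inferiority |
|---|---|---|
| 0 | 7.00 | 2.5% |
| 5% | 6.65 | 3.6% |
| 10% | 6.30 | 5.1% |
| 20% | 5.60 | 9.5% |

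With SD 22 and the same 124 per arm (SE 2.794), the last three rates are 3.3%, 4.4% and 7.2%.

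**3. As-treated against 2SLS.** Simulation with 10,000 runs per row, 124 per arm, SD 17 and a true effect of 7. It assumes that 10% cross over from repair of both tendons to FDP alone. The 10-point prognostic difference is also an assumption.

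| Underlying outcome of those crossing over | Mean ITT | Mean as-treated | Mean 2SLS | False NI: ITT | as-treated | 2SLS |
|---|---|---|---|---|---|---|
| No different | 6.26 | 6.98 | 6.96 | 5.6% | 2.4% | 2.7% |
| 10 points better | 6.31 | 5.18 | 7.02 | 4.9% | 13.0% | 2.7% |
| 10 points worse | 6.28 | 8.80 | 6.98 | 5.0% | 0.3% | 2.5% |

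The two estimators agree only when crossover is unrelated to prognosis. When it is related, as-treated can be worse than ITT or strongly conservative, while 2SLS stays near 2.5%.

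**4. What an ITT–CACE gap should mean.** With one instrument, one treatment variable, and the same participants and covariates in both regressions, the 2SLS estimate equals the ITT coefficient divided by the first-stage coefficient. In step 2 that gives 6.65/0.95, 6.30/0.90 and 5.60/0.80, each 7.00. The gaps due to compliance are 0.35, 0.70 and 1.40 points. These are small beside a standard error of 2.16, so a modest shift from different covariates or participants could hide or imitate them.

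**5. Analysis set.** The sample-size allowance implies up to 310 − 248 = 62 participants without a six-month score. Protocol 3.1 aims for at least 85% follow-up, which would be at most 0.15 × 310 ≈ 46. Those with an earlier score can contribute to the primary model but not to the CACE model as written.

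**6. Width of the CACE interval.** At d = 10% the standard error is 2.159 / 0.90 = 2.40. With a true difference of zero, the chance of excluding the margin is Φ(7/2.40 − 1.96) = 83%, against 90% for ITT.

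**The case against.** The strongest reply is that SAP 13.7.1 names its method completely: 2SLS, the instrument and the Stata command. A programmer who follows it cannot produce an as-treated analysis. That stands. A reader might infer from the gloss that an as-treated analysis will be run; the documents do not support this, and the clause is a wrong explanation of a correctly named method.

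On the model, ivregress takes one outcome time, so a repeated-measures model cannot be copied. Randomisation is stratified by site only (Protocol 5.5.1, SAP Section 10). Omitting nerve injury and anaesthetic type therefore does not bias an estimate that uses randomised assignment. It costs precision, leaves chance imbalance unadjusted and weakens comparability. A claim that the planned CACE is biased for this reason would go too far. What remains is that the omission is avoidable and that the baseline score is not identified.

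On the decision rule, a reader might infer that CACE must also exclude the margin because it was added to guard against a false claim. The protocol and SAP make ITT primary and only say that both analyses will be done. Gating is a preference, and step 6 shows its price.

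On crossover, a reader might infer that surgeons choose the operation in theatre. Protocol 4.6 and 4.14 say that treatment follows the allocation, which is made after final eligibility is confirmed in theatre. Crossover may be rare, and a link with injury severity would be inference. Likewise, the 20% attrition allowance does not predict that a fifth will be missing from the CACE.

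**Conclusion.** The concern holds as a contradiction in wording and an avoidable mismatch between models. It does not show that the primary analysis is wrong or that an invalid analysis is planned. The sample size is unaffected.

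The practical size depends on crossover. The inflated ITT error rates in step 2 need both a true effect exactly at the margin and appreciable net non-receipt; the as-treated results in step 3 also need crossover related to prognosis. With almost no crossover, a matched ITT and CACE would nearly coincide. The case for correction is that the analysis exists for the situation where crossover does occur, and in that situation its result could not be read cleanly as now specified.

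**What to change.** 1. In SAP 13.7.1, delete the clause beginning 'i.e.'. The 2SLS description can stand alone.
2. Include nerve injury, anaesthetic type, and both pre- and post-injury PEM scores in both stages, keeping the site-clustered standard errors.
3. Beside the CACE, report a six-month ITT linear regression on the same participants with the same covariates. The difference between these two then reflects compliance, and the difference between this regression and the primary mixed model shows the effect of model and analysis set.
4. Report the CACE interval against the same 7-point margin and state that it is supportive. First reconcile the direction: SAP 7.1 makes higher scores worse and SAP 13.2 uses the upper bound, while Appendix A treats higher scores as better and tests a lower bound against −7. Appendix A also gives the margin as six points before applying 7.

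I would not move the CACE into imputed data as a simple edit. SAP 13.7.2 triggers imputation only when more than 5% are excluded from the primary model, and it lists only baseline variables, so a separate provision would be needed.

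The cost is a short SAP amendment and slightly more analysis work, one extra regression and its table row. The covariates are already collected.

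### The site-clustered standard error in the CACE analysis has no small-cluster correction, so with few or uneven sites its interval is somewhat too narrow

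*SAP*

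**What the plan says.** SAP 13.7.1 specifies a two-stage least squares regression with allocation as the instrument, fitted with Stata's ivregress command. The outcome is the six-month PEM Hand Health Profile score and the only stated covariate is the baseline score. Site enters only through the variance: "with robust standard errors to account for clustering within site". The section does not mention a finite-sample option, a t reference distribution, a minimum number of sites or a site term in the mean model.

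SAP section 10 allocates individual patients 1:1, "using block randomisation stratified by study site with randomly varying block sizes". Site is the only stratification factor. The primary model in SAP 13.5 carries site as a random effect, so the CACE model handles site differently and gives no reason.

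The SAP explains why the CACE analysis exists: "In non-inferiority comparisons the ITT analysis could bias towards the null", which it says could produce a wrong claim of non-inferiority. Protocol section 3 plans up to 40 sites, and Protocol 3.1 sets a pilot target of ten. Neither document gives a minimum number of sites for the main analysis.

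**The concern.** A cluster-robust variance is built from one score total per site, so the number of sites, not the number of patients, governs how well it is estimated. With few sites it is biased downwards and noisy. Unequal site sizes lower the effective number of clusters further, and a normal critical value ignores the noise. The resulting interval is too narrow.

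Uneven recruitment is foreseeable. Protocol 4.11.1 describes staggered centre set-up, and the amendment history gives low-recruiting sites as a reason for simplifying the stratification. Forty is a ceiling, not a commitment.

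The CACE analysis is the plan's own guard against a false non-inferiority claim. If its interval falls short of nominal coverage, a CACE result that appears to confirm the primary analysis is less reassuring than it looks.

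**Working it through.** **Inputs from the documents.** One-sided alpha 0.025, power 90% and total 310 (SAP section 9: "For 90% power and alpha=0.025, 310 participants are required"); margin 7 points ("within a margin of seven points on the PEM"); SD 17; 20% attrition; 1:1 allocation in varying blocks within site (SAP section 10).

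**Reproducing the plan's figure.** Per arm, n = 2(1.960 + 1.282)² × 17² / 7² = 123.9, so 124. Total 248, and 248 / 0.8 = 310, an exact match. The analysed number for the check is therefore 248.

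**Assumptions not in the documents.** 95% compliance in each arm (5% crossover each way), site intraclass correlation (ICC) 0.05, site-size coefficient of variation 0 (equal) or 1 (uneven), baseline correlation 0.3, and block sizes 2, 4 and 6. The SAP does not state the critical value, so the normal value is also an assumption.

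**Method.** The true effect was set at the 7-point margin, with 6,000 simulated trials per setting (Monte Carlo error about 0.2 to 0.3 points for the rates shown). Let X hold treatment received and baseline score, and W the same with allocation in place of treatment received. The clustered variance is (W′X)⁻¹ [Σ_g u_g u_g′] (X′W)⁻¹, where u_g is the sum of w_i r_i over the patients in site g and r_i is the residual. It was computed with and without the factor G/(G − 1), where G is the number of sites. Non-inferiority was accepted when the 97.5% bound fell inside the margin. The fixed-effects version removed site means from all variables and used a robust variance.

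**False non-inferiority (%, nominal 2.5%).** The first range runs from with to without the factor.

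| Sites | Sizes | Clustered, normal value | Clustered with factor, t(G − 1) | Site fixed effects, robust |
|---|---|---|---|---|
| 40 | equal | 3.0–3.3 | 2.7 | 2.7 |
| 40 | uneven | 3.6–3.8 | 3.1 | 2.7 |
| 30 | equal | 2.9–3.2 | 2.5 | 2.5 |
| 30 | uneven | 3.4–3.8 | 2.9 | 2.5 |
| 20 | equal | 3.0–3.2 | 2.1 | 2.1 |
| 20 | uneven | 4.1–4.6 | 3.4 | 2.6 |
| 10 | equal | 3.8–4.3 | 2.1 | 2.5 |
| 10 | uneven | 5.1–6.0 | 3.3 | 2.4 |

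With ICC 0 and uneven sites the clustered interval gave 3.2–3.4% at 40 sites and 5.9–6.4% at 10. A separate simulation with ICC 0.03 gave 3.2–4.4% at 40 sites, 3.4–4.2% at 20 and 4.1–6.5% at 10, against 2.3–2.9% with site fixed effects.

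**Size of the bias in the standard error (uneven sites, ICC 0.05).** At 40 sites the mean clustered standard error was 2.18–2.22 against a true SD of 2.29, a ratio of 0.95 to 0.97. At 10 sites it was 1.95–2.06 against 2.21, a ratio of 0.88 to 0.93.

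**If the treatment effect varies between sites** (assumed SD 5 points, uneven sites):

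| Sites | Clustered, normal value | Clustered, t(G − 1) | Site fixed effects, robust |
|---|---|---|---|
| 40 | 2.9–3.2 | 2.6 | 3.3 |
| 10 | 6.5–7.4 | 4.6 | 7.7 |

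**The case against.** Several points on the other side are sound.

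- **Clustering by site is defensible.** A reader might infer that it is wrong because patients are individually randomised within site. The documents and the simulation do not support that. The number and inequality of clusters narrow the interval, and clustering gives some protection if effects differ between sites.
- **Ten sites is not the planned main analysis.** SAP section 12 says a trial stopped at the pilot is only described, so no CACE analysis would be run. At one patient per site per month, 10 sites over 22 months give 220 patients, short of 310. The main phase needs 230 / 14 = 16.4 per month, or about 17 sites. The range of 20 to 40 sites is the more relevant one. It is not guaranteed, because the final number is not stated and SAP Appendix C records a pilot restarted for 12 months with the same target of 80.
- **The decision rule does not use the CACE interval.** A reader might infer that the trial's own false non-inferiority rate rises. Appendix A ties acceptance to the SAP 13.5 model. If both analyses had to pass, the joint error could not exceed that of the primary analysis.
- **The CACE analysis may still be stricter than ITT.** With 5% crossover each way, a complier effect of 7 points dilutes to 7 × 0.90 = 6.3 under ITT. The standard error is 17√(2/124) = 2.16, so ITT accepts with probability Φ(−1.96 + 0.7/2.16) = Φ(−1.64), about 5.1%. The CACE rates at 20 to 40 sites are lower.

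These points limit the cause, the size and the consequence. They do not supply the missing correction: the interval as specified still falls short of its nominal level.

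**Conclusion.** The point holds as a gap in specification with a modest effect. Followed as written with a normal critical value, SAP 13.7.1 gives an interval whose false non-inferiority rate is about 3 to 4.6% for 20 to 40 sites and about 4 to 6.5% for 10, against a nominal 2.5%. The upper values come mainly from uneven site sizes. At 40 sites the standard error is only 3 to 5% too small even when sites are uneven.

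These figures rest on assumed compliance, ICC, site-size spread and critical value. The SAP leaves the critical value and the finite-sample factor open, so a corrected interval would also fit its text; naming the choice would settle it. The documents do not show that the trial's conclusion is affected, and they do not show that fixed effects are always the better choice.

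**What to change.** In SAP 13.7.1, pre-specify one of two options:

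1. Keep the site-clustered standard errors, and state the small-sample correction and t critical values on (sites − 1) degrees of freedom. This is the safer choice if treatment effects may differ between sites. With uneven sites it leaves some excess: 2.9–3.4% in the 10- to 40-site settings above. The cost is a slightly wider interval. At 20 sites the critical value is 2.093 instead of 1.960, about 7% wider; at 40 it is 2.023, about 3% wider.
2. Include site as fixed effects in both stages, with heteroskedasticity-robust standard errors. This restored 2.1–2.7% when effects did not differ between sites, but gave no protection when they did. It uses up to (sites − 1) degrees of freedom: 39 of 248 patients at 40 sites, where the average is 248 / 40 = 6.2 patients per site. The loss of precision in the simulation was small (SD of the estimate 2.33 against 2.29 with 40 uneven sites).

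Either option is one line of SAP text and code, recorded in the amendment log in SAP section 14.
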